## 2 Rationale and specific aims

This human laboratory study seeks to test the hypothesis that activation of nicotinic acetylcholine receptors (nAChRs) in the brain will reduce impulsive behavior in response to negative emotional cues as compared to neutral emotional cues. Because impulsive action during negative mood states is strongly correlated with impulsive aggression in both healthy individuals and individuals with schizophrenia (discussed below), our overarching, long-term goal is to determine whether nAChRs in general as well as specific nAChR subclasses might represent novel treatment targets to reduce impulsive aggressive behavior, a significant public health problem.

Nicotinic acetylcholine receptors are a large family of excitatory, pentameric, ionotropic, ligand-gated ion channels located throughout the brain and the remainder of the body. Their endogenous ligand is acetylcholine, yet this family is defined by their common activation by nicotine. Interestingly, anti-aggressive, or "serenic" effects of nicotine have been demonstrated across a number of animal models, including mice, rats, and non-human primates, and multiple human laboratory studies demonstrate an anti-aggressive effect of nicotine in humans. As detailed in section 3.1, our laboratory has also demonstrated that acute administration of nicotine at relatively low doses results in reduction of aggressive behaviors in mouse models. Because nicotine is active at all nAChRs, we explored this mechanism further and found that hippocampal alpha-7 nAChRs were both necessary and sufficient for nicotine's serenic effect. Consistent with these findings, there is substantial evidence in humans that reduction of alpha-7 nAChR signaling enhances aggressive behavior, including in individuals with 15q13.3

microdeletion syndrome, a genetic disorder resulting from the deletion of the region of chromosome 15 containing the gene coding for alpha-7 nAChRs. We have also translated these findings into human clinical populations. We recently demonstrated the safety and efficacy of transdermal nicotine to reduce aggression and irritability in young adults with autism spectrum disorder, described in section 3.2. This work, along with other previous case studies in humans, supports targeting nAChRs using transdermal nicotine to reduce aggressive behaviors.

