performed in 5 blocks of 32 trials, with 3 emotional blocks with angry/fearful/sad/disgust faces and 2 non-emotional blocks (Figure 1). Each stimulus is presented for 1 s with a 1 s interstimulus interval. In each block the subject is instructed on the go/no-go targets, each comprising 50% of the task stimuli, with instructions changing at the halfway point in each block. Each block contains two instructions. For example: Emotional blocks: go-angry/nogo-fear or go-fear/nogo-angry; Non-emotional blocks: go-male/nogo-female or go-female/nogo-male (Figure 2). Error rates and reaction times are recorded.

Figure 2 Emotional Go/NoGo schematic. Subjects are given a target instruction at the start of each block for 6 seconds. There is 1 second of blank screen between each 1 second stimulus presentation. In this schematic, the subject would press a key ("Go") when presented with the first stimulus (angry; green border represents the correct response is "Go". This border would not be present in the actual task), and withhold pressing a key for the second stimulus (sad; red border).

Subjects will be monitored for at least 30 minutes after patch removal to confirm the absence of side effects that would compromise their safety upon leaving the hospital.

Subjects will return for day 2 of testing not less than 5 days following day 1. On day 2, subjects will receive the treatment they did not receive on day 1. They will be asked a series of standard questions to assess for the presence of any side effects following their initial study day. If female, they will again be administered a urine pregnancy test to confirm the absence of pregnancy. The remainder of the procedure will be identical to day 1.

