## 12 Statistical considerations

#### 12.1 Power analysis

Power analysis for error rates and reaction times is based on effect sizes from previous studies of the Emotional Go/NoGo task in subjects with schizophrenia and our preliminary data from a secondary analysis of a clinical trial of the alpha-7 nicotinic agonist GTS-21. With a sample size of 25 subjects, we will achieve 80% power at  $\Box$ lpha = 0.05 to detect a difference from 35% to 10% in the omission error between two experimental conditions within a subject (expected correlation of 0.60) and to detect an effect size of 0.6 in the mean reaction times between the control and intervention conditions within a person using paired t-test at alpha = 0.05. The dropout rate in a similar published acute crossover study of schizophrenia patients was ~15%. We thus anticipate needing to enroll 30 subjects to result in 25 completers for an appropriately powered study. We will match this group with a healthy control sample of similar size.

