#### 12.2 Data analysis plan

Omission error rate will be analyzed using non-linear mixed effects modeling of a binary outcome omission error (0/1), while reaction time will be analyzed with a linear mixed effects model. In both models, there will be a random effect for subject, a primary fixed independent predictor treatment condition (nicotine or placebo), an independent adjustment variable block valence (emotional vs. non-emotional task), and the interaction of the latter two predictors to examine whether the omission error rate or reaction time between two treatment conditions is moderated by the valence. Significance will be established at alpha = 0.05.

We expect nicotine will reduce error rates in control blocks consistent with previous reports of improved attention with acute dosing of transdermal nicotine. We expect to find an interaction between valence and treatment such that performance improves with nicotine to a significantly greater extent in negative valence blocks. We further expect this increase to be more prominent in individuals with schizophrenia than in healthy controls. We expect salivary nicotine concentration, which is proportional to serum nicotine, will correlate with improvement in response inhibition. Based on previous findings in the Emotional Go/NoGo task, we do not expect to find an effect of antipsychotic exposure, as measured by chlorpromazine equivalents.

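### Section 12.2 predicts a larger valence-dependent nicotine benefit in schizophrenia than in healthy controls, but neither model has a diagnostic-group term and no between-group test is planned

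*Combined protocol and SAP*

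**What the plan says.** Section 12.2 specifies two mixed models, one for omission error coded 0/1 and one for reaction time. Each has a random effect for subject and a fixed effect of nicotine versus placebo. To these it adds "an independent adjustment variable block valence (emotional vs. non-emotional task), and the interaction of the latter two predictors". Diagnostic group is not among the terms.

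The next paragraph states the expected findings: "We expect to find an interaction between valence and treatment such that performance improves with nicotine to a significantly greater extent in negative valence blocks". It continues: "We further expect this increase to be more prominent in individuals with schizophrenia than in healthy controls".

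Section 12.1 powers within-subject contrasts in 25 schizophrenia completers and then says of the controls: "We will match this group with a healthy control sample of similar size". It gives no power figure for a comparison between groups. Section 2 states the central hypothesis, that nicotinic activation "will reduce impulsive behavior in response to negative emotional cues as compared to neutral emotional cues", and this does not mention a group difference.

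**The concern.** The increase expected to be more prominent in schizophrenia is the valence-dependent benefit of the preceding sentence. The prediction is therefore that the treatment × valence effect differs by diagnosis, and no coefficient in either model represents that.

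The plan also leaves open how the two groups enter the analysis. Powering the schizophrenia sample alone and then adding matched controls hints at separate fits, but the text never says so. Under either reading the group prediction has no planned test, although a control sample of about the same size is recruited. The gap leaves room for a comparison of the form significant in patients, not significant in controls, which does not test a group difference.

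**Working it through.** **1. The plan's own figure.** For reaction time, section 12.1 claims 80% power with 25 subjects at effect size 0.6 by paired t-test. With two-sided alpha 0.05 the noncentral t gives 82.1%, and 80% power is reached at 0.584, so the claim reproduces. Enrolment also does: 25 / (1 − 0.15) = 29.4, hence 30. Both figures concern a contrast within subjects, not a comparison of groups.

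**2. Hypothesis against model.** Let D be each subject's treatment × valence contrast: the nicotine-minus-placebo difference in emotional blocks minus the same difference in non-emotional blocks.

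- Section 2 and the first prediction concern the mean of D. The treatment × valence term estimates it.
- The group prediction concerns mean D in schizophrenia minus mean D in controls. Neither model has a term for it.
- A pooled fit returns one D averaged over diagnosis. Separate fits return two, and the plan names no comparison of them.

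**3. Power of the missing test.** Assume 25 completers per group, two-sided alpha 0.05, and a two-sample t-test on D with 48 degrees of freedom and noncentrality d × √(25/2). The group difference d, in SDs of D, is an assumption.

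| d | Noncentrality | Power | Completers per group for 80% |
|---|---|---|---|
| 0.3 | 1.06 | 18% | 176 |
| 0.6 | 2.12 | 55% | 45 |
| 0.81 | 2.86 | 80% | 25 |

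The 95% CI half-width is 2.011 × √(2/25) = 0.57 SD.

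**4. What a comparison of two significance verdicts would do.** Suppose the true effect is the same in both groups and each within-group test has power p. Exactly one group is significant with probability 2p(1 − p). At p = 0.8 this is 2 × 0.8 × 0.2 = 32% (patients only: 16%). At p = 0.5 it is 50% (patients only: 25%).

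**5. Random effects once group is added.** Section 6.2 describes the task as "performed in 5 blocks of 32 trials, with 3 emotional blocks with angry/fearful/sad/disgust faces and 2 non-emotional blocks", with half the stimuli go targets. This gives at most 3 × 32 × 0.5 = 48 emotional and 2 × 32 × 0.5 = 32 non-emotional go trials per session. Set the trial SD to 1 and let s be the between-subject SD of D. The sampling variance of one subject's D is v = 2/48 + 2/32 = 0.104. A trial-level model with only a random intercept uses v where v + s² is needed, so its Type I error is roughly 2Φ(−1.96 × √(v/(v + s²))).

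The simulated figures below are for reaction time, with no true group difference. The trial-level and subject-level columns assume subject SDs of 0.3 for treatment and for valence. The last two columns apply the random-intercept model to four subject-by-condition means per person.

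| s | Formula | Trial level, intercept only | Subject-level t | Means, SDs 0.3 | Means, SDs 0.15 |
|---|---|---|---|---|---|
| 0 | 5.0% | 4–5% | 5% | 0.03% | 1.5% |
| 0.15 | 7.5% | 7% | 5% | 0.2% | 2.3% |
| 0.3 | 15.1% | 14% | 5% | 0.8% | 4.8% |
| 0.5 | 28.8% | 26–28% | 5% | 3.4% | 9.5% |

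The formula runs slightly high because the fitted residual variance absorbs part of s². At s = 0.3 the CI half-widths are 1.96 × √(0.08 × 0.104) = 0.18 for the intercept-only model and 2.011 × √(0.08 × 0.194) = 0.25 for the subject-level comparison, where 0.08 = 2/25 and 0.194 = v + 0.3². With condition means the intercept-only test is conservative when treatment and valence effects vary as assumed in the first means column. It can become liberal when they vary less and s is large. The subject-level t-test holds 5% in every setting tried.

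**The case against.** The sentence is one of several expectations in section 12.2. Those on salivary nicotine and chlorpromazine equivalents have no model either. It is not a named endpoint, and the trial is powered only within subjects. This stands, and it limits the weight of the point. It does not supply a test. Section 12.3 shows that the plan can mark a comparison as hypothesis-generating when it means to, as it does for sex, and the group prediction carries no such label.

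Four stronger readings are tempting, and the documents do not support them.

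- *The main hypothesis cannot be tested.* It can: the treatment × valence term covers the hypothesis in section 2.
- *The plan yields no estimate of the group difference.* Under separate fits to independent groups, the difference of the two interaction estimates and its standard error, √(SE₁² + SE₂²), follow by arithmetic. What is missing is a prespecified comparison.
- *The investigators intend to compare significance verdicts.* No section proposes this. The 32% and 16% show what such a comparison would do, not what is planned.
- *A random subject effect makes the interval too narrow.* Section 12.2 does not say whether that effect is an intercept only. It gives no unit of analysis for reaction time, and section 12.1 refers to mean reaction times. With condition means the error can go the other way. The binary omission model was not computed, so none of the Type I error figures carry over to it.

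**Conclusion.** The point holds as a gap in the analysis plan that should be closed, at moderate weight. A directional group hypothesis is stated, a control sample of similar size is recruited, and neither a model term, a between-group test nor a rule on pooling is given. This rests on the text alone and needs no numerical assumption.

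The sizes do rest on assumptions. The power figures (18%, 55%, and 80% at about 0.81 SD) assume 25 completers per group and group differences that the documents do not give. The inflation to about 7% to 28% for an intercept-only model applies to trial-level reaction times with a subject SD of 0.15 to 0.5 trial SD in the treatment × valence effect. It should not be read as a property of the plan as written, which contains no group term and leaves the reaction-time unit open.

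**What to change.** Before treatment order is unblinded, amend section 12.2 as follows.

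- Fit both groups in one model per outcome, adding diagnostic group and all its interactions with treatment and valence. For reaction time, a two-sample comparison of the subject-level contrast D does the same job more simply.
- Name group × treatment × valence as a secondary test. Report it as an estimate with a 95% CI, and take the within-group treatment and treatment × valence contrasts from the same model.
- State that any claim of a group difference rests on that term, not on significance in one group only.
- State the unit of analysis for reaction time. For any trial-level model, of reaction time or omission, include by-subject slopes for treatment, valence and their interaction, and give a fallback if the model does not converge, such as uncorrelated slopes.

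The cost is wording only, since diagnosis is already known for every subject. The downsides are four more fixed coefficients per model (from 4 to 8), more variance terms to estimate, possible convergence trouble in the binary model, and a test whose low power should be stated openly.

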#### 12.3 Inclusion of men and women

We do not expect significant difficulties in patient recruitment based on previous studies with similar patient populations conducted in the [name] Lab. Men and women will be included in this study. Unlike highly sexually dimorphic rodent aggression, multiple studies find no significant gender difference in physical aggression amongst inpatients with schizophrenia. Given these previous findings and the above power analysis, it is outside the scope or resources of this focused study to power sufficiently to include sex/gender as a formal variable in our experimental design. However, all efforts will be made to recruit similar numbers of men and women to the study, final reported data will be disaggregated by sex/gender, and *hypothesis-generating* comparative analyses will be performed that can be pursued in future, *hypothesis-testing* prospective studies. Previous studies of nicotine for cognition in schizophrenia enrolled men and women, but no differences in their response to drug were reported. The inclusion of drug plasma levels can mitigate pharmacokinetic-based differential responses between men and women, and will be done in the proposed study.

## 13 Privacy/confidentiality issues

Data obtained from human subjects will be confidential and accessed only by members of the study team with appropriate IRB/HIC and HIPAA training, as assured by standard training protocols at Vanderbilt University Medical Center. Data is maintained and secured in locked file cabinets or on encrypted, password protected computers, located in locked offices, and following Health Insurance Portability and Accountability Act (HIPAA) guidelines and the policies and procedures of Vanderbilt University and Vanderbilt University Medical Center. Individuals will be identified by a numerical code that will be kept separate from study data.

#### 14 Follow-up and record retention

The estimated duration of the data collection phase of the study is four years. Identifying information will be deleted (in the case of digital data) or destroyed by shredding using clinical shredding bins by the principal investigator or trained study personnel at the conclusion of the data collection phase of the study. The non-identifying study data will be transferred to a portable hard drive and stored in a locked filling cabinet. Non-identifying data stored in the above manner will be retained indefinitely. Only the PI, study coordinator, and research staff will have access to the information.

